4.1. Demographics

Demographic information (year of birth, age, sex, race) will be recorded at screening, unless disallowed by local regulatory agencies. Demographics (including but not limited to age, age group (19-64, ≥ 65), sex, and race, if allowable per local regulatory authorities) and baseline characteristics will be presented in summary tables.

For US, UK, and Canadian participants who will be performing the optional WLA, additional demographic information will be collected. The optional WLA data will be analyzed and reported outside of this SAP.

Demographic information collected at Screening will be summarized by group and overall for all participants in the safety population and listed. Descriptive statistics will be calculated for the following continuous demographic characteristics: age (years), screening and Day 1 pre-dose weight (kg), screening height (cm), and screening body mass index (BMI) (kg/m²). Frequency counts will be tabulated for the categorical variables sex, race, and ethnicity.

4.2. Diagnostics Characterization

A diagnostic characterization form will be completed in the electronic case report form (eCRF) only at screening, week 97 and week 197 (if applicable for symptomatic participants in the optional Part 2 OLE). It will also be completed for any asymptomatic participant who becomes symptomatic during the course of the study; for these participants, the diagnostic characterization form will be completed only at the first visit in which they exhibit clinical symptomatology.

Diagnostic characterization data will be summarized for the Safety population and will be presented in a data listing.

4.3. Medical History

All relevant medical history and information regarding underlying diseases will be coded using the Medical Dictionary for Regulatory Activities (MedDRA), version to be delineated in the CSR.

Medical history data will be summarized by system organ class (SOC), preferred term (PT) for the Safety population. Medical history data will be presented in a data listing.

4.4. Admission Criteria Deviation

Admission criteria deviation data (violations of the inclusion/exclusion criteria) will be presented in a data listing.

4.5. Pharmacogenomic Measurements

A blood sample will be collected during Part 1 at screening for DNA extraction to enable analysis via whole genome sequencing (WGS) to identify common and rare genetic variants that are predictive of response to study drug, are associated with progression to a more severe disease state, are associated with susceptibility to developing AEs, or can increase the knowledge and understanding of disease biology.

Pharmacogenomic data will not be analyzed or reported in the CSR.

5. Treatments and Medications

5.1. Prior and Concomitant Medications

All concomitant medications used by a participant from informed consent through Study Completion or ET visit, whichever is later, will be recorded in the participant's eCRF and coded using the World Health Organization Drug Dictionary (WHO-DD), version to be delineated in the CSR. The minimum requirement is that drug name, total daily dose, route, frequency of dosing, indicated use, and the dates of administration are to be recorded. This will include all prescription drugs, herbal products, vitamins, minerals, vaccines, topical medications, and over-the-counter medications. Any changes in concomitant medications also will be recorded in the participant's eCRF.

Any restricted medication must have been stopped as required by the study inclusion and exclusion criterion (Protocol Sections 4.2.1 and 4.2.2 respectively); participants who start these medications during the study may be withdrawn from study treatment at the discretion of the sponsor's medical monitor.

A medication will be considered as concomitant if the end date and time of administration is after start of administration of study drug. If the date and time of administration contains partial information such that the attribution of concomitant administration cannot be ruled out then it will be considered as concomitant. A medication will be considered as prior if the start and stop date and time of administration is prior to the start of administration of study drug. A medication started prior to study drug and continuing during the study will be considered as concomitant.

The number and percentage of participants taking prior and concomitant medications will be summarized for each level of ATC (Anatomical-Therapeutic-Chemical) and preferred drug name, and alphabetically sorted for participants in the Safety population.

Prior and concomitant medications will be presented in a data listing.

5.2. Medical and Surgical Treatment Procedures

Medical and surgical treatment procedure data will be presented in a data listing.

5.3. Study Drug Administration

Study drug administration data will be summarized for the Safety population. The summary will include duration of exposure to study drug (in days), the number of doses received, treatment compliance, number of doses interrupted, discontinued, and total dose (mg) received.

Duration of exposure to study drug (days) is defined as the total number of days a participant is exposed to AL001 and will be calculated as the total number of days from the first dose date (Study Day 1) to the last dose date + 28 days, regardless of any temporary interruptions in study drug administration. 28 days is the study treatment administration (IV) interval.

Treatment compliance will be defined as the total cumulative received dose (mg/kg) divided by the total cumulative expected dose (mg/kg) up to the last dose, and then multiplied by 100. The total cumulative expected dose will be the sum of the expected doses while they are on study treatment across all planned study days, up to the date of withdrawal, if participant discontinued study drug early.

The function is as follow:

Treatment Compliance=100×(total cumulative received dose (mg/kg))/(total cumulative expected dose (mg/kg))

Study drug administration data will be presented in a listing. Any drug administration interruption and reasons will be listed.

6. Safety Analysis

All analyses of safety data will be conducted using the Safety population. All safety data will be listed.

6.1. Adverse Events

An AE is defined as any untoward medical occurrence in a participant enrolled into this study regardless of its causal relationship to study drug.

A treatment-emergent AE (TEAE) is defined as any event not present before exposure to study drug, or any event already present that worsens in either intensity or frequency after exposure.

An imputation will be performed for AEs with incomplete (partial) dates to determine whether an AE is treatment emergent.

For AEs with a partial start date:

- If the year is unknown, then the AE start date will be the date of first dose.
- If the month is unknown, then:
 - If the year matches the year of the first dose date, then the month and day of the first dose date will be imputed.
 - Otherwise, ‘January’ will be assigned.
- If the day is unknown, then:
 - If the month and year match the month and year of the first dose date, then the day of the first dose date will be imputed.
 - Otherwise, ‘01’ will be assigned.

For AEs with a partial end date:

- If the year is unknown, then the date assigned will be the last visit date.
- If the month is unknown, then the month from the last visit date will be assigned.
- If the day is unknown, then the last day of the month will be assigned.

If the imputation approach results in a start date that is after a known end date, then the start date will be set to the day before the end date. If the imputation approach results in an end date that is before a known start date, then the end date will be set to the day after the start date.

An AE with completely missing onset and end dates, or with the start date missing and an end date later than the first dose date of study drug, will be considered to be treatment emergent. In addition, an AE with the start date missing and incomplete end date with the same or later month and year (or year alone if month is not recorded) as the first dose date of study drug will be considered treatment emergent.

The relationship of AE to study drug will be classified as Not Related or Related by the Investigator. If the relationship information is missing, the AE will be considered Related in the summary but will be presented as missing in the listings.

The severity of AEs will be classified as Mild, Moderate, Severe, Life-threatening, or Death by the Investigator. If the severity information is missing, the AE will be considered Severe in the summary but will be presented as missing in the listings.

Adverse Events will be coded by SOC and PT according to MedDRA, version to be delineated in the CSR.

All summary tables will include counts and frequency of participants and number of events. Subject incidence rate of AEs will be summarized by SOC and PT and for PT only. The summary will be provided separately by overall descending incidence rate and then by alphabetical order. A separate summary will be provided by alphabetical order for SOC and PT. A participant with 2 or more occurrences for the same AE, the subject will be counted only once in that level using the worst severity (for the severity table) or the most related (for the relationship to study drug table). Percentages will be based upon the number of participants in the Safety population.

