1.3.1. Known Risks of the Drug Class

Immune Response: Monoclonal antibodies like AL001 may be associated with a potential immune response, such as hypersensitivity or hypersensitivity-like reactions, including severe anaphylactic reactions.

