5.1.2. Infusion-Related and Injection-Related Reactions

All participants will be monitored for infusion-related reactions or injection-related reactions during the infusion/injection and immediately afterwards for at least 60 minutes.

Injection-related reactions can be localized at the site of the injection or systemic and should be treated per institutional guidelines. If a participant experiences a mild infusion-related reaction,

the infusion should be halted. Once the reaction has resolved, the infusion rate will be resumed at half the most recently used rate (e.g., from 60 mL/hr [1.0 mL/min] to 30 mL/hr [0.5 mL/min]). The infusion should be stopped immediately for any participant who experiences a moderate to severe infusion-related reaction (e.g., fever or chills), and the participant should receive aggressive symptomatic treatment. The infusion should not be restarted before all symptoms have disappeared, and then it should be restarted at half of the initial rate. The infusion should not be resumed if there is a second occurrence or if the participant experiences any of the following events: mucosal tissue involvement, airway compromise, or symptomatic hypotension with systolic blood pressure <90 mm Hg measured in the supine position.

In addition, in the event of an infusion-related reaction, a sample of blood should be obtained for PK serum and ADA assessment of AL001, and testing should be performed for C-reactive protein, tryptase, and Interleukin 6 (IL-6). Further details regarding infusion-related reactions are provided in the IB.

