7.5. Reporting Adverse Events

All AEs and SAEs must be recorded and reported, regardless of cause or relationship, that occur after the participant signs informed consent through the Part1/Part 2 EOS or Safety Follow-up visit, whichever is later. Any unresolved AEs and SAEs will be followed up through satisfactory clinical resolution. Additionally, SAEs considered related to study treatment that occur at any time should be reported by the investigator regardless of the AE/SAE collection window.

Definitions describing what is and is not considered an AE are provided in [Section 7.1](#).

Information to be collected includes the following:

- Event term
- Time and date of onset
- Investigator-specified assessment of severity and relationship to study drug
- Time of resolution of the event

- Seriousness
- Any required treatment or evaluations
- Outcome

The Medical Dictionary for Regulatory Activities (MedDRA) Version 21.1 or later will be used to code all AEs.

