8.4.2.4. Adverse Events

Adverse events will be recorded as described in [Section 7.7](#) and will be coded to system organ class and preferred term according to MedDRA, Version 21.1 or later. A TEAE is defined as described in [Section 7.1](#). The following AE summaries will be reported by system organ class, preferred term, and combined participant status and dementia type at baseline:

- TEAEs
- Treatment-related TEAEs
- TEAEs by relationship to study drug
- TEAEs by severity
- SAEs
- TEAEs leading to study drug discontinuation
- TEAEs leading to study discontinuation

For safety reporting, any clinically significant changes in MRI after dosing relative to baseline will be evaluated by the investigator and will be included in the eCRF as AEs. A separate analysis of AEs identified through MRI will not be conducted.

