In most instances, study drug should be administered at the investigational site. In the event the participant is unable to have study drug administered at the investigational site (i.e., due to participant or site restrictions related to Covid-19) study drug administration for the third and subsequent infusions may be performed “at home” (i.e., at the participant’s home or other suitable location) by a home healthcare provider who has appropriate training and expertise in IV administration. Study drug administration for the first and second infusion must be conducted at the investigational site, at home study drug administration for subsequent infusions may only be performed with Medical Monitor approval.

The following procedures must be performed for each at home study drug administration:

Before study drug administration:

- Home healthcare provider will record vital signs, including systolic and diastolic BP, pulse, body temperature, and respiratory rate (recorded after the participant has been resting for at least 5 minutes in the supine position)
- Home healthcare provider will conduct an assessment^{1,2} to include evaluation of general appearance, skin, EENT, head and neck, extremities, abdomen, and respiratory, cardiovascular, neurological, and musculoskeletal systems
- Home healthcare provider will conduct a review of concomitant medication(s)
- Home healthcare provider will record any AEs (signs and symptoms) which may have occurred since previous visit
- Home healthcare provider will contact the investigative site by phone or video (investigator or designee) to review findings from the assessment, adverse events and concomitant medications
- Home healthcare provider must receive email confirmation from the investigative site to proceed with study drug administration, prior to initiating study drug administration.

During study drug administration:

- Approximately 15 and 45 minutes after initiating study drug administration, monitor vital signs, including systolic and diastolic BP, pulse, body temperature, and respiratory rate²
- Monitor for infusion-related reactions or injection-related reactions³
- Record any AEs (signs and symptoms)

After study drug administration

- Record vital signs, including systolic and diastolic BP, pulse, body temperature, and respiratory rate (recorded within 15 minutes after the end of infusion)
- Monitor for infusion-related reactions or injection-related reactions for at least 90 minutes post-infusion³

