6.1.1. Incidence of Adverse Events

An overall summary of AEs will be presented and will include summaries for the following:

- Any TEAE
- Any Treatment-Related TEAE
- TEAEs by Severity
- Treatment-Related TEAEs by Severity
- Any SAE
- Any Treatment-Emergent SAE
- Any Treatment-Related TESAE
- Any TEAE Leading to Study Drug Discontinuation
- Fatal TESAE

In addition, all TEAEs will be summarized by SOC and PT.

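### The SAP plans no table that counts each participant once across infusion-related, hypersensitivity and anaphylactic reactions, so their combined incidence can be understated

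*SAP*

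**What the plan says.** **The risk.** Protocol 1.3.1 says antibodies of this type "may be associated with a potential immune response, such as hypersensitivity or hypersensitivity-like reactions, including severe anaphylactic reactions". It does not mention infusion reactions; Protocol 5.1.2 and 7.9 deal with those. Infusion-related reactions (under stated conditions) and anaphylaxis appear among the reasons for stopping study drug in Part 1 (4.3.1.1) and Part 2 (4.4.1).

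**The tables.** Protocol 8.4.2.4 lists seven summaries: "The following AE summaries will be reported by system organ class, preferred term, and combined participant status and dementia type at baseline". SAP 6.1 states: "Subject incidence rate of AEs will be summarized by SOC and PT and for PT only". SAP 6.1.1 gives nine categories for the overall summary, none of them for reactions, and adds: "In addition, all TEAEs will be summarized by SOC and PT". SAP 6.1.2 to 6.1.5 add relationship, severity, seriousness and study drug discontinuation.

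**Other reaction-related outputs.** SAP 5.3 tabulates the number of interrupted doses and lists the reasons. SAP 6.7 leaves reaction-triggered ADA samples out of the ADA summary and lists the affected participants' data separately.

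**How events are recorded.** Protocol 7.1 asks investigators for a diagnosis in preference to symptoms where they can give one. Appendix 3 tells the home provider to "record any AEs (signs and symptoms", and has abnormal findings sent to the site as AEs for entry in the EDC. Protocol 7.5 collects "Time and date of onset" for every AE.

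**The concern.** In an open-label study of an IV antibody given up to 50 times (25 doses in each part), a reader of the report will ask three things about reactions: how many participants had one, at which dose, and whether ADA-positive participants had more. AE incidence, nature and severity, and ADA incidence, are primary safety endpoints of Part 1. The protocol collects what is needed to answer, but no planned summary brings it together.

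Tables by single preferred term also depend on how each event was worded. If one participant's reaction is entered as a diagnosis and another's as its component symptoms, they land in different rows, and no row gives the number of participants who reacted. The SAP introduction classes any analysis done after database lock as post hoc, so a grouping added then would be chosen with the results in view.

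**Working it through.** **1. The plan's own figure.** The only quantitative safety input is the sample-size statement (Protocol 8.1, SAP 2.1): the chance of at least one finding among 40 participants, 1 − (1 − p)^40.

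| True rate p | Stated | Recomputed |
|---|---|---|
| 0.1% | 3.9% | 3.92% |
| 1% | 33.1% | 33.10% |
| 5% | 87.1% | 87.149% |
| 10% | 98.5% | 98.52% |

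The figures reproduce. They concern an event counted once per participant. Splitting a reaction across terms does not hide it, because it still appears in some row. What is lost is the participant count.

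**2. What each planned output gives.**

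| Output | Pooled across reaction terms, once per participant | By dose number | By ADA status |
|---|---|---|---|
| Preferred-term row (SAP 6.1) | No | No | No |
| SOC row (SAP 6.1) | Only if the terms share an SOC, and mixed with unrelated events | No | No |
| Severity table (SAP 6.1.3) | No | No | No |
| Interrupted doses (SAP 5.3) | No; a reaction after the infusion ends interrupts nothing | Listing only | No |
| ADA data for affected participants (SAP 6.7) | Listing only | Listing only | Listing only |

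**3. Why the pooled count cannot be recovered from the rows.** Let r1, …, rk be the participant counts in k reaction-related rows. The number of participants with at least one such event lies between max(r) and the smaller of sum(r) and 40.

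Illustration with assumed counts, since the documents give neither a reaction rate nor a coding split: take k = 4 rows of 1/40 each.
- Lower bound: one participant with four symptoms, 1/40 = 2.5% (exact 95% CI 0.1 to 13.2).
- Upper bound: four participants with one symptom each, 4/40 = 10.0% (exact 95% CI 2.8 to 23.7).

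Both cases produce the same preferred-term rows. Quoting the largest row can understate the incidence, and adding the rows can overstate it. The exact limits are Clopper-Pearson: the 2.5% point of Beta(x, 40 − x + 1) and the 97.5% point of Beta(x + 1, 40 − x).

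**4. Where symptom-level entry can arise.** Home infusion is allowed from the third dose, so up to 25 − 2 = 23 Part 1 doses per participant could qualify. It needs COVID-19-related restrictions and Medical Monitor approval, and the documents do not say how often it was used. Protocol 5.1.2 also describes a moderate to severe reaction through example symptoms and gives no case definition. SAP 6.7 needs a rule for deciding who had reaction signs and symptoms in order to build its listing, and states none.

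**The case against.** The strongest reply is that the existing tables already do most of the work.

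- **A reader might infer that no table gives a reaction count or its severity.** The documents do not support that. Protocol 5.1.2 treats an infusion-related reaction as a named, graded entity and 7.1 prefers the diagnosis. A diagnosed reaction will therefore have a preferred-term row, and will appear in the tables by severity and relationship and, where applicable, by seriousness and discontinuation.
- **Symptom entry rests on an exception.** Under Appendix 3 the home provider must contact the site about any AE seen during or after the infusion, so the investigator can still supply a diagnosis. Nothing requires a recognised reaction to be entered as separate symptoms.
- **A reader might infer that the C-reactive protein, tryptase and IL-6 results go unreported** because SAP Table 8-1 omits them. SAP 6 commits to listing all safety data, which covers them.
- **A reader might try to put a probability on the understatement.** If 4 reactors each have one term from m equally likely terms, the chance that every row shows 1/40 is m(m−1)(m−2)(m−3)/m^4, which is 19.2% for m = 5 and 41.0% for m = 8. With two different symptoms each it becomes 0% for m = 5 (8 entries cannot fit in 5 rows without a repeat) and (15 × 6 × 1)/28^3 = 0.4% for m = 8. The result is driven by the assumption and should not be quoted as a size.
- **Background.** Protocol 1.3.2 reports no important identified risks. With about 40 participants, a reader could work through the listings.

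All of this stands as a limit on the point. It does not supply a pooled count, a count by dose number or a count by ADA status. Even if every reaction were coded as a diagnosis, infusion-related, hypersensitivity and anaphylactic terms would still sit in separate rows.

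**Conclusion.** The point holds as a gap in the summary tables. Data capture is not at fault, and individual diagnosed reactions will be visible. Neither document plans an output that counts each participant once across the reaction terms, or that tabulates reactions by dose number or ADA status. The pooled incidence can be understated where reactions are entered as signs and symptoms. The size is unknown, because the documents give no reaction rate, no share of home infusions and no coding split. The Investigator's Brochure and the iDMC charter are not available here and might contain a definition. The change is a low-cost improvement to the summary of a primary safety endpoint.

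**What to change.** In SAP 6.1, before database lock, pre-specify one grouped table of participants with at least one infusion-related or hypersensitivity reaction, each counted once.

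- **Events included:** TEAEs coded as infusion-related, hypersensitivity or anaphylactic reaction; plus TEAEs on a symptom list fixed before lock, with onset from the start of an infusion to 60 minutes after its end. Sixty minutes is the minimum observation time common to site infusions (at least 60, Protocol 5.1.2) and home infusions (at least 90, Appendix 3). It is an analysis window only and changes no monitoring or treatment rule.
- **Display:** n/N with exact 95% CI, by worst severity, by dose number and by ADA status. For dose number, use the participants infused at that dose as the denominator, because SAP 2 reports high attrition. State how ADA status is defined per participant, since SAP 6.7 summarises ADA only by visit, and whether reaction-triggered samples count.
- **Missing onset time:** state a rule. SAP 6.1 imputes partial dates but not clock times.

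The cost is SAP wording and one table. AE onset times are already collected. The window assumes that infusion start and end times are recorded, which the vital-signs rule in SAP 6.3 already requires. The drawback is that the symptom list may capture a few unrelated events. Showing the coded-reaction count separately from the symptom-based additions would make that visible.
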